3.5 Sample size

The ArthroCaP study has been designed as a proof-of-concept study, hypothesis-generating, with exploratory objectives. Based on the original recruitment rate in the main SPOC study, we expected to be able recruit in the sub-study ≥ 150 of the planned 388 SPOC participants. Although exploratory, enrolling ≥ 150 participants would give us a power of $\geq 80\%$ to detect an association between moderate-severe CPSP at 6 months and ≥ 2 point decline in MoCA at 1 year, with an Odds Ratio of 2.5-3.0 when we consider some residual correlation between independent variables (i.e., $R^2 \leq 0.3$ even after removing collinear covariates. This was based on the assumptions that 20% of the study participants will experience ≥ 2 point decline in MoCA at 1 year (considering the possibly younger age and different surgery representation in our study compared to NeuroVISION-1), and that 30% will present moderate-severe CPSP at 6 months (see sample size calculation for the main SPOC study).

Due to the disruptions to recruitment secondary to the pandemic, we modified our target sample size to 100 patients, aware that the study will provide preliminary nondefinitive data to inform future research. This is consistent with the intent of the catalyst grant that supports the study.

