4. IMPORTANCE OF THE STUDY

“My father hasn’t been quite the same since his surgery...” As doctors, and as children, many of us have had and reported such experience. Anesthetic-related mortality has decreased 100-fold over the last 100 years. However, when asked about their fears related to undergoing major surgery with general anesthesia, people, across different ages, indicate ‘brain damage’ and ‘memory loss’ as main concerns, much more frequently than perioperative death.³⁷ Moreover, the literature shows that, even with only a partial understanding of the concept of likelihood, most older people would not choose a treatment when the expected outcome is survival, if associated with cognitive and functional impairment.^{38 39} CPSP is highly prevalent in older people undergoing surgery, and in particular major orthopedic surgery; in the older surgical populations, also persistent postoperative cognitive dysfunction is highly prevalent. Both these conditions are associated with reduced autonomy and increased burden to patients, caregivers, and healthcare systems.

On the other side, the existing literature shows a decrease in quality of life in people with chronic pain waiting for >6 months for assessment;⁴⁰ and that people waiting for their major joint surgery tend to report that their waiting time is contributing significantly to the deterioration of their health.⁴¹ Likewise, the current experience with COVID and the deferral of elective surgeries is bringing to our attention what holding such treatment might mean to older people with chronic conditions. Our study will provide preliminary data on the role of chronic pain, and chronic pain medications, in the impact of surgery on older people’s cognitive abilities, and on the underlying mechanisms. It will inform larger confirmatory studies, and finally the design of interventions to enhance the benefits of surgery.

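### The stated power of at least 80% at n = 150 does not follow from the protocol's own inputs (about 46% to 74% at an assumed two-sided 5%), and the current target of 100 has no power or precision figure

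*Combined protocol and SAP*

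**What the plan says.** Section 3.5 gives one power statement: "enrolling ≥ 150 participants would give us a power of $\geq 80\%$ to detect an association" between moderate-to-severe CPSP at 6 months and a MoCA decline of 2 points or more at 1 year, "with an Odds Ratio of 2.5-3.0 when we consider some residual correlation between independent variables", with R² of at most 0.3. The two assumed rates are that "20% of the study participants will experience ≥ 2 point decline in MoCA at 1 year" and "that 30% will present moderate-severe CPSP at 6 months". The section states no significance level, sidedness, formula or allowance for loss to follow-up.

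Because of the pandemic, "we modified our target sample size to 100 patients", "aware that the study will provide preliminary nondefinitive data to inform future research". No power, detectable odds ratio or interval width accompanies that number. Section 4 says of the study: "It will inform larger confirmatory studies".

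**The concern.** With 150 participants, a 20% outcome rate gives only 30 expected events, split across exposure groups of 45 and 105. That is thin for an odds ratio of 2.5 to 3.0, more so once R² up to 0.3 shrinks the effective sample.

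This is the only power statement in the plan, and the error is in the favourable direction. A team planning a confirmatory study from these inputs would take 150 as enough. For the size now planned, a reader has no figure for how wide the interval will be, and so no guide to reading a null result.

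**Working it through.** **Inputs from section 3.5.** n = 150; OR = 2.5 or 3.0; overall outcome rate P = 0.20; exposure prevalence B = 0.30; R² from 0 to 0.3. **Assumed:** two-sided 5% (z = 1.96) and no loss to follow-up.

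**Risks.** Solve 0.7·p0 + 0.3·p1 = 0.20 with p1 = OR·p0 / (1 − p0 + OR·p0):
- OR 2.5: p0 = 0.1526, p1 = 0.3105, difference 0.1579
- OR 3.0: p0 = 0.1429, p1 = 0.3333, difference 0.1905

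**Power.** Hsieh formula for logistic regression with a binary covariate, effective n = n(1 − R²):

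z_β = [ (p1 − p0)·√(n(1 − R²)(1 − B)) − z_α·√(P(1 − P)/B) ] / √( p0(1 − p0) + p1(1 − p1)(1 − B)/B )

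The second term of the numerator is 1.96 × √(0.16/0.3) = 1.96 × 0.7303 = 1.431. The denominator is 0.793 for OR 2.5 and 0.801 for OR 3.0.

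| n | OR | R² | First term | z_β | Power |
|---|---|---|---|---|---|
| 150 | 2.5 | 0 | 0.1579 × √105 = 1.618 | 0.235 | 59.3% |
| 150 | 2.5 | 0.3 | 0.1579 × √73.5 = 1.353 | −0.098 | 46.1% |
| 150 | 3.0 | 0 | 0.1905 × √105 = 1.952 | 0.650 | 74.2% |
| 150 | 3.0 | 0.3 | 0.1905 × √73.5 = 1.633 | 0.252 | 59.9% |
| 100 | 2.5 | 0 | 0.1579 × √70 = 1.321 | −0.139 | 44.5% |
| 100 | 2.5 | 0.3 | 0.1579 × √49 = 1.105 | −0.411 | 34.0% |
| 100 | 3.0 | 0 | 0.1905 × √70 = 1.594 | 0.203 | 58.0% |
| 100 | 3.0 | 0.3 | 0.1905 × √49 = 1.333 | −0.122 | 45.1% |

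The plan's 80% is therefore not reproduced at n = 150.

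**Solving the same formula the other way.**
- N for 80% power: 253 (OR 2.5) and 175 (OR 3.0) at R² = 0; 361 and 250 at R² = 0.3.
- Odds ratio detectable with 80% power: 3.27 (R² = 0) to 4.12 (R² = 0.3) at n = 150; 4.26 to 5.70 at n = 100.

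**More favourable readings at n = 150.**

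| Reading | OR 2.5, R² 0 / 0.3 | OR 3.0, R² 0 / 0.3 | OR 3.0 reaches 80% only if R² is below about |
|---|---|---|---|
| Two-sided 5%, 20% as unexposed risk | 65% / 51% | 81% / 67% | 0.03 |
| One-sided 5%, 20% overall | 70% / 58% | 83% / 71% | 0.08 |
| One-sided 5%, 20% as unexposed risk | 75.5% / 63% | 88% / 77% | 0.23 |

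An odds ratio of 2.5 stays below 80% in every row, even at R² = 0. No row gives 80% at R² = 0.3.

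**Is the formula pessimistic?** A Wald calculation at n = 150 gives 44% to 74%. Simulation (6,000 logistic fits per setting) gives 57% and 73% at R² = 0, and 42% and 56% at R² = 0.3, for OR 2.5 and 3.0. The simulated values are slightly below the formula.

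**Loss to follow-up.** If 10% to 20% lacked the 12-month MoCA (an assumption), 150 enrolled would leave 135 to 120, with power from about 39% to 70%.

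**Precision at n = 100.** Var(log OR) = [1/(70·p0(1 − p0)) + 1/(30·p1(1 − p1))] / (1 − R²). For a true OR of 2.5:
- R² = 0: 0.1105 + 0.1557 = 0.266, SE 0.516, expected 95% CI about 0.91 to 6.9
- R² = 0.3: 0.266/0.7 = 0.380, SE 0.617, expected 95% CI about 0.75 to 8.4

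For a true OR of 1, the intervals are about 0.34 to 2.9 and 0.28 to 3.6. These are large-sample approximations with about 20 expected events.

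**The case against.** **Alpha is unstated, so the figure could rest on a level not tested above.** With one-sided 10% and 20% as the overall rate, power is 80.5% at OR 2.5 with R² = 0 and 80.8% at OR 3.0 with R² = 0.3, and the detectable odds ratio runs from 2.48 to 2.95. That fits the stated range well. But nothing in the documents supports so unusual a level. If it was used, it had to be declared.

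**The range may be paired.** The sentence can be read as a detectable odds ratio of 2.5 at R² = 0 rising to 3.0 at R² = 0.3, so that 46% and 74% are corners never claimed. This is a fair reading, but it gives 59% and 60% at two-sided 5%, and 76% and 77% with one-sided 5% and 20% as the unexposed risk. It still falls short.

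**The consequence is limited.** The 150 belongs to a superseded target. The study is described as proof-of-concept, and no decision rule depends on the 80%. Section 3.6 analyses objective 1 with mixed-effects models of scores over time; logistic regression on the 2-point decline is named only under objective 3. Power for the mixed models may differ from the figures here. These points stand and bear on severity. They do not make a sentence in the current section 3.5 correct. The absence of a figure for 100 would, taken alone, be missing detail and not an error.

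**Conclusion.** The concern holds. With the stated 20%, 30% and R² up to 0.3, and two-sided 5% assumed, power at n = 150 is 46% to 74%, or about 60% if odds ratio and R² are paired. No 5% reading, one-sided or two-sided, supports 80% across the stated range. At the current target of 100, the same inputs give 34% to 58%.

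The result rests on CPSP being a yes/no exposure, as its 30% prevalence implies, on the assumed alpha, and on complete follow-up; losses would lower power further. It should be fixed, but the exploratory purpose and replaced target keep it from being more serious.

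**What to change.** In section 3.5, correct or withdraw the 80% statement, and state alpha, sidedness and method. If it is corrected at two-sided 5%, write about 46% to 60% at R² = 0.3 and 59% to 74% at R² = 0, for odds ratios of 2.5 to 3.0 at n = 150.

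For the target of 100, give one of these:
- approximate power (34% to 45% at R² = 0.3; 44% to 58% at R² = 0) with the detectable odds ratio (about 4.3 to 5.7); or
- the expected confidence-interval width.

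Label the figures as large-sample approximations before loss to follow-up, and say that they refer to the binary 12-month outcome and not to the mixed-effects models of objective 1.

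The cost is protocol wording only: no additional participants, procedures or analyses. The one downside is a less favourable stated figure.

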3.6 Statistical analyses

Baseline characteristics will be summarized through descriptive statistics, i.e. mean (standard deviation), median (interquartile range [IQR]), or number (%) as appropriate.

Objective 1. We will first evaluate the primary study objective modeling longitudinal changes in pain scores (independent variable) and changes in cognitive/neuropsychological scores (dependent variable) over time (4 weeks, and 3, 6, and 12 months after surgery) using multilevel (mixed effects) regression models, considering time points nested within patients.³⁶ Secondly, in mixed effects models, we will specifically look at whether experiencing moderate-severe persistent pain at 3 months after surgery (or at 6 months after surgery) predicts subsequent decline in cognitive performance (i.e. at 6 and 12 months, or at 12 months).⁹ Models will be adjusted for relevant covariates, including baseline characteristics (at the patient level, e.g. age, sex, comorbidity index, and anxiety/depression level) and pain medications as time-varying variables. We will adopt a parsimonious approach in covariates selection, based on clinical relevance and removing collinear covariates (i.e., variance inflation factor > 2.5) according to pre-specified priorities. We will use the same statistical approach to look at the association between satisfaction (measured with the SAPS instrument) and cognitive performance.

Objectives 2. We will explore our objective 2a, analyzing separately change in MST scores and changes in other cognitive performance measures. Bonferroni correction of alpha values will be adopted to adjust for multiple comparisons. For the biomarker study (objective 2b), we will similarly model mixed effects regression models to evaluate how the biomarker levels change over time and how these changes correlate with changes in pain, satisfaction, and cognitive performance. We will also analyze whether biomarkers levels at baseline (before surgery), and

right after surgery (or at 4-6 weeks after surgery) predict cognitive changes/decline at 6 and 12 months.

Objective 3. To evaluate the role of coping abilities and expectations, as measured by the SPOC questionnaire, we will first analyze the association between baseline SPOC and baseline cognitive performance in a traditional multivariable linear regression analysis; similarly, we will analyze the association between early postoperative (4-6 weeks) SPOC and cognitive performance, after adjusting for baseline measurements. Then we will analyze whether preoperative and postoperative SPOC predict cognitive decline at 6 and 12 months using linear and logistic (i.e. with ≥ 2 point decline in MoCA as binary outcome) regression models.

All the analyses for all the objectives will be first conducted in the overall sample of study participants. As additional analysis, we will explore whether there is a signal for any subgroup effect based on the type of surgery performed, i.e., knee versus hip arthroplasty. We will undertake such exploratory subgroup analyses as long as both subpopulations reach at least 30% of representation.

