3.4 Measurements

Patients who agree to participate in the ArthroCaP sub-study while the recruitment in SPOC is ongoing will undergo all the procedures and measurements outlined in the protocol for the main study. In particular, participants are assessed at baseline for their socio-demographics data, comorbidities, Physical Frailty Phenotype, health-related quality of life (EQ-5D), anxiety and depression (Hospital Anxiety and Depression Scale [HADS]), pain, and pain medication. Pain scores (based on a numerical pain scale) and pain medications are assessed at baseline, and then 4-6 weeks, 3 months, 6 months and 12 months after surgery. The SPOC instrument is administered at baseline and repeated at 4-6 weeks after surgery. The presence and severity of CPSP and satisfaction (SAPS) are measured at 3, 6, and 12 months. Changes in health-related quality of life and clinical complications are also monitored and collected over time. For TKA and THA patients approached after the termination of the recruitment in SPOC, these measurements will be described in the ArthroCaP informed consent form and conducted by the ArthroCaP study team

using ArthroCaP-specific case report forms (CRFs), as done for the cognitive/neuropsychological assessment.

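### The time-ordered Objective 1 models use pain only as moderate-severe yes/no; the numerical score from the same visits should be added as a continuous exposure

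*Combined protocol and SAP*

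**What the plan says.** Section 3.6 evaluates Objective 1 in two steps. The first uses mixed-effects models of change over time, "modeling longitudinal changes in pain scores (independent variable"), with changes in cognitive scores as the dependent variable. The second is lagged and asks "whether experiencing moderate-severe persistent pain at 3 months after surgery (or at 6 months after surgery) predicts subsequent decline in cognitive performance". Outcomes are taken at 6 and 12 months for the 3-month exposure, and at 12 months for the 6-month exposure.

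Section 3.4 describes two kinds of pain measurement. One is the score: "Pain scores (based on a numerical pain scale) and pain medications are assessed at baseline, and then 4-6 weeks, 3 months, 6 months", and also 12 months. The other is CPSP, listed in its own sentence: "The presence and severity of CPSP and satisfaction (SAPS) are measured at 3, 6, and 12 months". No cut-off for moderate-severe is given, and nothing says which of the two measurements supplies the category.

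Section 3.5 assumes for planning that "30% will present moderate-severe CPSP at 6 months". It gives no corresponding figure for 3 months. The target sample size has been lowered from at least 150 to 100, and the study is described as exploratory.

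**The concern.** Section 1 describes the relation between pain and cognition as possibly running in both directions. The lagged step is where the plan puts pain before cognition, so it carries most of the weight on whether pain precedes decline. Its only version of pain is a category holding about 30 of 100 participants (30% × 100, if the 6-month assumption holds). A yes/no exposure treats everyone on the same side of the line alike and cannot show whether decline grows with pain intensity.

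The first step keeps pain undichotomised, but it relates change to change and does not set out a time order. Appendix I schedules pain but no cognitive testing at 3 months, so the 3-month score has no cognitive result from the same visit. Prediction of later cognition is its natural use, and there it does not appear. A graded association could be missed or estimated less precisely than the collected data allow, in a study whose purpose is to inform larger ones.

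**Working it through.** **Plan's own figure.** The plan gives no figure for information lost through a yes/no exposure. Its one power statement already assumes a binary exposure: at least 80% power with N ≥ 150, "with an Odds Ratio of 2.5-3.0", covariate R² up to 0.3, 30% exposed, and "20% of the study participants will experience ≥ 2 point decline in MoCA at 1 year". I could not reproduce it at R² = 0.3. I used the Hsieh logistic-regression formula for a binary covariate, two-sided 0.05 (assumed, as the plan states no alpha here):

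N = [1.96·√(P(1−P)/B) + 0.842·√(p0(1−p0) + p1(1−p1)(1−B)/B)]² / [(p0−p1)²(1−B)(1−R²)]

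With B = 0.30, P = 0.20 and odds ratio 3.0, p0 = 0.143 and p1 = 0.333, so N = 250. Power at N = 150 is 60%, or 67% if the 20% is read as the rate in the unexposed. For odds ratio 2.5 it is 46% or 51%. This is a separate matter and neither supports nor weakens the present point.

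**Information kept by a yes/no exposure.** Assume that the category is the score split at a cut and that the association is linear in the score. The share kept is then the squared correlation between the score and the indicator.

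- *Normal score, 30% above the cut:* φ(z)²/[p(1−p)] with z = 0.524 and φ(z) = 0.3477 gives 0.1209/0.21 = 0.576. Loss 42%.
- *Rounded-normal 0-10 score, 30% at 4 or more:* loss 38% at SD 1.5, falling to 29% at SD 3.
- *Skewed or zero-inflated 0-10 scores, cut at 4 or 5, 22-36% exposed:* loss about 16-39%. The lowest case can be checked by hand. Put half the patients at 0 and spread the rest evenly over 0-10, with a cut at 4. The exposed share is 0.5 × 7/11 = 0.318, the variance is 17.5 − 2.5² = 11.25, and the covariance is 0.5 × 49/11 − 2.5 × 0.318 = 1.432. The share kept is 1.432²/(11.25 × 0.318 × 0.682) = 0.84. Loss 16%.
- *Normal score, covariates explaining 30% of it:* kept 0.576 × 0.7/(1 − 0.576 × 0.3) = 0.487. Loss 51%.
- *Effect present only above the cut:* the category loses nothing. A linear term in a normal score would then lose the 42%.

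The score shapes, the cut-offs and the linear form are my assumptions.

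**Illustrative power at n = 100.** This takes one unadjusted correlation, two-sided 0.05, Fisher z: power = Φ(√97·atanh(r√k) − 1.96), where k is the share of information kept.

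| Share kept (k) | r = 0.30 | r = 0.25 |
|---|---|---|
| 1 (full score) | 86% | 71% |
| 0.75 | 75% | 58% |
| 0.576 | 63% | 47% |

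For example, with r = 0.30 and k = 0.75, r√k = 0.260, atanh = 0.266, and 0.266 × 9.849 − 1.96 = 0.659, so power is 75%. At k = 0.84, the mildest shape tried, the same formula gives 79% and 63%. A simulation with a normal score and r = 0.25 gave 72% with the score and 48% with the split. Keeping 58-75% of the information at n = 100 is equivalent to analysing the full score in 58-75 patients.

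**The case against.** The strongest reply is that the category is the research question. Objective 1 names CPSP as an exposure, section 1 states the hypothesis in terms of CPSP, and section 3.5 bases its power statement on moderate-severe CPSP. Undichotomised pain comes first in the two-step analysis, so the plan has both a score version and a clinical version. It also claims only preliminary, exploratory results. All of this stands. The CPSP contrast is legitimate and should stay, and any loss is confined to the second step. What remains is that neither step uses the score to predict later cognition. An exploratory study gains from a dose-response estimate, so its exploratory status is no reason to leave one out.

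Some stronger readings are tempting but not supported:

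- A reader might infer that the plan takes the numerical score and cuts it in two. Section 3.4 lists CPSP presence and severity separately, and no cut-off or derivation is given, so the category may come from its own item.
- A reader might take the first model to pair pain and cognition at the same visits. Section 3.6 does not state the pairing, and Appendix I rules it out at 3 months. The lag structure is simply unspecified.
- A reader might quote a fixed percentage as the loss in the whole study. The loss depends on linearity and on a score distribution that the documents do not give.

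The power figures describe a single unadjusted correlation. The planned analysis is a covariate-adjusted mixed model with, for the 3-month exposure, outcomes at two visits. They show the order of magnitude only.

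**Conclusion.** The point holds as an omission in section 3.6: the lagged models use pain at 3 or 6 months only as yes/no, while a numerical score from the same visits goes unused for prediction. Given a roughly linear association, about 30% exposed and a category that behaves like a split of the score, the loss is 42% for a normal score and about 16-39% for plausible 0-10 shapes. It is larger (51%) for a normal score after adjustment at R² = 0.3, and nil for a threshold effect at the cut. The 30% is a 6-month planning assumption, and applying it to the 3-month exposure is a further assumption.

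This is not an error that invalidates Objective 1, and it does not follow that the CPSP contrast should give way to the score as lead analysis. That would be a debatable change of estimand. The supported conclusion is that the continuous version belongs beside it, at little cost.

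**What to change.** In section 3.6, Objective 1, make two changes.

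1. Add the 3-month (or 6-month) numerical pain score as a continuous exposure, per point, in the same lagged mixed models with the same covariates. Include one squared or spline term to check linearity, and report the result alongside the retained moderate-severe CPSP contrast.
2. Define moderate-severe, and state whether the category is derived from the numerical score or from the separately recorded CPSP severity.

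The cost is a few sentences in the analysis section and one additional exploratory model for each exposure time, with no new data. A linear term is less sensitive if the effect exists only above a threshold, and the retained CPSP contrast covers that case.

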1. BACKGROUND AND RATIONALE

Surgery has been associated with short and long-term changes in cognition (postoperative cognitive dysfunction, POCD).^{1,2} The literature shows that most often patients show POCD during the first 1-3 months after surgery, and then recover.³ However, in the recently published NeuroVISION study, up to 30% of 65 years old or older people undergoing different types of noncardiac surgery presented a decline of ≥ 2 points in their Montreal Cognitive Assessment (MoCA) score at 1 year after surgery compared to prior to surgery.⁴ A ≥ 2 points in MoCA score has been shown to correspond to cognitive decline based on formal neuropsychological testing and to be of clinical significance.^{5,6} The risk factors and determinants of POCD are poorly understood.⁷

Chronic pain has been associated with cognitive dysfunction, in particular memory and concentration deficits.⁸ The existing literature on chronic pain in general supports the hypothesis of a bidirectional interaction between pain and cognitive processing.⁸ However, in a longitudinal community-based study, a history of persistent pain (of any origin) at baseline was associated with memory decline, and even dementia, over 10 years of follow-up.⁹ We hypothesize that a similar association might exist between post-surgical pain, and in particular chronic post-surgical pain (CPSP) and POCD (**objective 1**). A surgical population including older ages and with an expected high prevalence of CPSP, like patients undergoing total knee and hip replacement,¹⁰ seems a suitable population to evaluate this association. In this population, up to 23% of hip replacement and 34% of knee replacement surgery patients experience long term pain after surgery.¹¹ The long-term need of analgesic therapy, and in particular, the chronic use of opioids in patients with CPSP, could also play an independent role in mediating the association between CPSP and cognitive changes. Overall, the existing literature on the association between CPSP and POCD, including the role of long-term opioid use, is very scanty and controversial.¹¹⁻¹³

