2. OBJECTIVES

The overarching objective of the ArthroCaP study is to explore the interplay between postoperative pain and self-reported recovery (i.e. satisfaction), coping abilities/expectations about surgery, and postoperative COGNITIVE trajectories in ≥ 50 years old people undergoing elective total knee arthroplasty (TKA) or total hip arthroplasty (THA).

The specific objectives of the ArthroCaP study are:

1. to explore the association of CPSP, long-term opioid use, and a multi-domain measure of patient satisfaction, with POCD, measured as changes over time of the performance at the Montreal Cognitive Assessment (MoCA) score, and at additional neuropsychological testing.
2. to explore whether postoperative cognitive changes are associated with changes in neurogenesis correlates (a) and in neurotrophic factors levels (b), and whether this association is mediated by changes in pain, mobility, and satisfaction
3. to explore the association between coping strategies/expectations before and after surgery, as measured by the SPOC questionnaire, and cognitive changes after surgery; and to explore the correlation between changes in SPOC and cognitive changes from preoperative to 4-6 weeks after surgery.
4. to qualitatively explore lived experiences of pain, mobility and aging, including resilience, expectations and satisfaction with surgery, in patients undergoing TKA or THA across different ages and comorbidities.

The current protocol and ethics submission describes methods and seek ethics approval for specific objectives 1-3. Objective 4 will be covered in a separate protocol and ethics application.

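### Long-term opioid use is an objective 1 exposure without a declared model, and the lagged CPSP models do not say which visit's pain medication they adjust for

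*Combined protocol and SAP*

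**What the plan says.** Section 2 sets objective 1 as "to explore the association of CPSP, long-term opioid use, and a multi-domain measure of patient satisfaction, with POCD". Section 1 gives the reason for including opioids: "the chronic use of opioids in patients with CPSP, could also play an independent role in mediating the association between CPSP and cognitive changes". Section 4 presents the study as a source of early evidence on long-term pain medication as well as on chronic pain.

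Section 3.4 says that "pain medications are assessed at baseline, and then 4-6 weeks, 3 months, 6 months and 12 months after surgery", and Appendix I schedules a general pain-medication item at the same five visits. The word opioid does not occur in section 3 or in Appendix I.

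Section 3.6 declares three analyses for objective 1:

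- a mixed model with pain score over time as the independent variable;
- lagged mixed models asking whether moderate-to-severe pain at month 3 (or month 6) "predicts subsequent decline in cognitive performance (i.e. at 6 and 12 months, or at 12 months";
- for the remaining exposure, "We will use the same statistical approach to look at the association between satisfaction (measured with the SAPS instrument) and cognitive performance".

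All are adjusted for baseline characteristics and for "anxiety/depression level) and pain medications as time-varying variables".

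**The concern.** Two things are at stake.

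First, an exposure named in the lead objective has neither an analysis definition nor a model in which it is the exposure. If the definition is chosen after the data are seen, a reader cannot tell whether the reported opioid result is the planned one. With few users, the result is also likely to be sensitive to that choice.

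Second, the lagged CPSP coefficient is likely to be read as the overall association between persistent pain and later cognition. Whether it is depends on which visit supplies the medication value, and the plan does not say. Section 1 itself puts opioid use on a possible path from CPSP to cognition, so adjusting for later medication may take out part of what the model is meant to show.

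**Working it through.** The documents give no figure for opioid use to reproduce. The check is a comparison of the text, one identity, and a precision calculation on assumed inputs.

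**1. Exposures against declared models**

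| Exposure in objective 1 | Data scheduled | Exposure model in section 3.6 |
|---|---|---|
| CPSP / pain | yes | yes (longitudinal and lagged) |
| Satisfaction (SAPS) | yes | yes (same approach) |
| Long-term opioid use | general pain medication, 5 visits | none |

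Drug class, duration, visits and coding are not stated for the third row.

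**2. Medication visits relative to the exposure visit**

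| Lagged model | Before exposure | Same visit | After exposure |
|---|---|---|---|
| CPSP at 3 months, cognition at 6 and 12 | baseline, 4-6 weeks | 3 months | 6 and 12 months |
| CPSP at 6 months, cognition at 12 | baseline, 4-6 weeks, 3 months | 6 months | 12 months |

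The usual meaning of a time-varying covariate is the value at each outcome visit, which falls in the last column. In the second model each participant has one outcome visit, so calling the covariate time-varying does not identify a visit at all.

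**3. What later medication does to the CPSP coefficient**

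In a linear model, with the other covariates held the same:

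coefficient without later medication = coefficient with it + d × b

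Here d is the covariate-adjusted difference in later medication use between participants with and without CPSP, and b is the medication coefficient. Neither is in the documents, so the shift d × b cannot be sized. A simulation with invented effects shows only the mechanism. It set the direct CPSP effect at -0.5, b at -1.0 and d at 0.1, 0.2 and 0.3:

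- expected overall coefficient: -0.5 - 0.1 = -0.60; -0.5 - 0.2 = -0.70; -0.5 - 0.3 = -0.80;
- simulated, adjusting for 6-month medication: -0.598, -0.698, -0.800;
- simulated, adjusting for 12-month medication: -0.498, -0.500, -0.498.

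The choice of visit changes what is estimated. These values are not a forecast for this study.

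**4. Precision of an opioid exposure model**

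95% CI half-width at one visit, in SD of the cognitive score:

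1.96 × sqrt(1/n1 + 1/(N - n1)) × sqrt(1 - r²) / sqrt(1 - R²)

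- N = 100, the revised target in section 3.5.
- R² = 0 or 0.3; the upper value is from section 3.5, "when we consider some residual correlation between independent variables".
- n1 = 5 to 20 opioid users (assumption).
- r = correlation of baseline with follow-up cognition: 0, meaning no baseline adjustment, or 0.6 to 0.7 (assumption).
- No dropout.

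| Users | R²=0: r=0 | r=0.6 | r=0.7 | R²=0.3: r=0 | r=0.6 | r=0.7 |
|---|---|---|---|---|---|---|
| 5 | 0.90 | 0.72 | 0.64 | 1.07 | 0.86 | 0.77 |
| 10 | 0.65 | 0.52 | 0.47 | 0.78 | 0.62 | 0.56 |
| 20 | 0.49 | 0.39 | 0.35 | 0.59 | 0.47 | 0.42 |

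Example: 5 users, r = 0, R² = 0 gives 1.96 × sqrt(1/5 + 1/95) = 1.96 × 0.459 = 0.90. With r = 0.6 this is 0.90 × 0.8 = 0.72.

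Precision is low throughout, and adjustment for baseline cognition improves it materially.

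**The case against.** The strongest reply is that medication sits in every objective 1 model, so a pain-adjusted medication coefficient will be available, and that this speaks to the independent role proposed in section 1. This stands in part: it would be wrong to infer that the study yields nothing on medication. But the coefficient is for analgesics in general, with unstated coding, and no sentence declares it as the opioid result.

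A second reply is that section 1 is ambiguous between an independent and a mediating role, and that objective 1 lists opioid use beside CPSP. If opioid use is a parallel exposure or a confounder, adjusting for it is defensible. This also stands. A reader might infer that time-varying adjustment is simply an error, and the documents do not support that. What they support is that the estimand is left open and that one plausible choice does not give the overall association.

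A reader might also infer that medication will be lost through the rule on "removing collinear covariates (i.e., variance inflation factor > 2.5) according to pre-specified priorities". A variance inflation factor of 2.5 corresponds to R² = 1 - 1/2.5 = 0.60 on the other covariates. The documents give no reason to expect that for medication. The R² of at most 0.3 in section 3.5 applies after collinear covariates are removed, so it settles nothing either way.

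Finally, the main SPOC protocol and the case report forms are not among the documents and may define the medication item. That could supply coding. The exposure model for objective 1 would still belong in this plan. The study is exploratory, which lowers the stakes but does not supply the missing model.

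**Conclusion.** The concern holds in this form. One of the three exposures in objective 1 has no definition and no declared model, although the medication data are scheduled at five visits. The lagged CPSP models are adjusted for medication from an unstated visit. If that visit follows the exposure, and if opioid use partly mediates the association, the coefficient is not the overall association.

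The first part rests on the text alone. The second depends on those two conditions, and its size cannot be derived from the documents; any percentage put on it would come from assumed inputs. Neither part invalidates an exploratory study, but both change what it can report, so the plan should be amended before outcome data are examined.

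**What to change.** **Lagged CPSP models.** State which visit's medication value is used. Report as the overall association a model adjusted for baseline cognition, preoperative covariates including baseline analgesic/opioid use and, where postoperative medication is used at all, only values recorded before the exposure visit. Report the planned model with time-varying medication beside it, labelled *medication-adjusted*. It should not be called a direct effect, because later pain may affect both medication and cognition.

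**Opioid exposure.** Confirm that the forms record opioids separately, then define long-term opioid use for analysis from the data already collected. Declare one exploratory exposure analysis with MoCA as the lead outcome:

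- 3-month status for cognition at 6 and 12 months, in a mixed model adjusted for baseline cognition and preoperative covariates, including baseline pain;
- 6-month status for cognition at 12 months, in a linear regression with the same adjustment, since there is one outcome row per participant and a random intercept cannot be identified.

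Fit each with and without postoperative pain up to the exposure visit, and give 95% CIs. Set any minimum number of users before outcome data are examined, allowing for the precision gained from baseline cognition, and report descriptively below it.

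**Cost.** SAP wording, one definition, and for MoCA about six further fits: two CPSP models without later medication, plus two opioid lags × two versions = 4. No new data collection is needed if the forms separate opioids. The downsides are more exploratory estimates, low precision at 100 participants, and residual confounding by pain severity. Without postoperative pain in the model, opioid use can stand in for CPSP; with it, part of the association may be adjusted away. With few users the opioid results may be descriptive only.
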